4. Women of childbearing potential (based on medical history) must consent to use a medically accepted method of birth control (e.g., condoms and spermicide, oral contraceptive, Depo-Provera injection, contraceptive patch, tubal ligation) or abstain from sexual intercourse during the time they are in the study and using transdermal nicotine.
5. If current or past diagnosis of bipolar disorder, eligible if:
 - a. No psychotic features
 - b. MADRS: total score less than 8 (past 4 weeks), suicidal item score less than 1 (past 4 weeks)
 - c. Y-MRS: total score less than 8 (past 4 weeks), irritability, speech content, disruptive or aggressive behavior items score less than 3 (past 4 weeks)
 - d. No psychiatric hospitalization or Emergency Room visits for psychiatric issues in the past 6 months
 - e. No aggressive or violent acts or behavior in the past 6 months
6. Able to communicate fluently in English.
7. Capable of giving written informed consent, which includes compliance with the requirements and restrictions listed in the combined consent/HIPAA form.

4. Key Exclusion Criteria

Subjects who self-report and/or present with the following criteria will not be eligible to participate in the study.

Smoking Behavior:

1. Current enrollment in a smoking cessation program, or use of other smoking cessation medications in the last month or plans to do either in the next 2 months.
2. Daily use of chewing tobacco, snuff and/or snus, or electronic cigarettes.

Alcohol/Drugs:

1. Self-report current alcohol consumption that exceeds 25 standard drinks/week over the past 6 months. Subjects will be told to limit or avoid the use of alcohol while in the study to avoid any adverse reactions to the study medication.
2. Current untreated and unstable diagnosis of substance dependence (eligible if past use and if receiving treatment and stable for at least 30 days). Current untreated and unstable diagnosis of substance abuse requires Study Physician approval.
3. A positive urine drug screen for cocaine, amphetamines, methamphetamines, PCP, barbiturates and ecstasy (MDMA) at Intake, or any testing session (see Measures and Table 1 for details). Participants believed to have a false-positive result may continue in the study, with investigator approval.

Medical:

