1. Females who self-report current pregnancy, planning a pregnancy during the study, or currently breastfeeding/lactating. All female subjects of child-bearing potential shall undergo a urine pregnancy test at the Intake, Baseline, PQ-Testing and 24-H Testing sessions.
2. Current diagnosis of unstable and untreated major depression, as determined by self-report & MINI (eligible if stable for at least 30 days).
3. Current or past diagnosis of psychotic disorder, as determined by self-report or MINI.
4. Suicide risk as indicated by at least one of the following on the MINI/CSSRS (the PI &/or PM (LCSW) will be consulted to assess safety and determine eligibility in cases close to the eligibility cutoffs):
 - a. Current suicidal ideation (within 30 days of enrollment)
 - b. Two or more lifetime suicide attempts or episodes of suicidal behavior
 - c. Any suicide attempt or suicidal behavior within 2 years of enrollment
5. Self-reported kidney and/or liver disease or transplant untreated/unstable or within the past 6 months.
6. Heart/Cardiovascular disease (e.g., angina, coronary heart disease, stroke, etc.) in the past 6 months.
7. Type-1 or type-2 diabetes.
8. Uncontrolled hypertension (BP systolic greater than 159 and/or diastolic greater than 99)*.
9. Liver function tests more than 20% outside of the normal range; Gamma-glutamyl Transpepsidase (GGT) values more than 20% outside of the normal range. If Albumin/Globulin ratios are 20% outside of normal range the abnormal value will be evaluated for clinical significance by the Study Physician and eligibility will be determined on a case-by-case basis.
10. Renal disease or renal dysfunction (e.g., serum creatinine levels ≥ 1.5 mg/dL [males], ≥ 1.4 mg/dL [females]).
11. A blood glucose level less than 70 mg/dl at any visit.

* Participants presenting with SBP greater than 159 mmHg and/or DBP greater than 99 mmHg at the Intake visit will be instructed to sit quietly for 10 minutes. Then the participant will have a second blood pressure reading taken after a 10-minute period. If, after the second reading the SBP greater than 159 mmHg and the DBP greater than 99 mmHg, the individual will be ineligible to participate, unless determined otherwise by the Study PI/Co-I or Study Physician, upon review.

Medication:

1. Current use or recent discontinuation (within the past 14 days) of any of the following medications:
 - a. Anti-anxiety or panic disorder medications (e.g., clonazepam, alprazolam).

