To ensure a high level of retention and adherence in this trial we will: 1) educate subjects about the benefits of protocol compliance; 2) schedule in-person sessions at convenient times (e.g., evenings); and 3) provide modest financial compensation for session completion and transportation costs.

Referral Bonus Program

Participants who achieve their final study visit (Day 23) will be given the opportunity to receive a small bonus for referring others to the program. If the person who is referred completes the initial eligibility phone screen, regardless of outcome, the study participant will be awarded \$20 per referral, for a maximum of 3 referrals (\$60).

[figure not shown]
STUDY DESIGN

1. Phase

N/A

2. Design

We propose to conduct a randomized, placebo-controlled, parallel arm study with one between-subjects factor of medication (low dose, high dose, placebo). Once eligibility is confirmed after Intake, subjects will attend a clinic visit (day 0) to establish baseline smoking rate, mood, and cognition. Subjects will then be randomized to one of three groups (low dose: 500 mg, high dose: 1500 mg, or placebo) and will complete 4 additional sessions (days 7, 14, 21, 23) to assess side effects, smoking rate, mood, craving, and withdrawal (Figure 1). Cognitive function will also be assessed on days 21 and 23. Subjects will be instructed to refrain from smoking for 24 hours prior to the laboratory session on day 23 (Figure 1). Following FDA guidelines, the dosing regimen for metformin extended release (XR) will be 500 mg q.d for the low dose. For the high dose, the dosing regimen will be: 500 mg q.d (days 1-7); 1000 mg q.d (days 8-14); 1500 mg q.d (days 15-23).

3. Study Duration

Estimated length of time to enroll all subjects and complete the study

Enrollment will start in March 2016. We estimate that we will need to telephone screen 660 smokers to enroll 160 HIV-smokers into the study. We expect a drop-out rate of 30% based on prior experience and expect to have 54 HIV- smokers complete the study. In addition, we will telephone screen 400 HIV+ smokers to enroll 90 and have 30 HIV+ smokers complete the study. We estimate enrolling 4-5 smokers per month.

Length of a subject’s participation time in study

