Blood pressure will be measured at all subsequent in-person visits. If participants present with elevated blood pressure (i.e., systolic blood pressure greater than 159 and/or diastolic blood pressure greater than 99) at any subsequent visit, the staff will follow the same steps listed above. If, after the second reading, systolic blood pressure remains greater than 159 and/or diastolic remains greater than 99, the Study Physician or Study PI will be consulted to discuss whether the participant should continue taking the study medication. Research staff will follow up with the participant accordingly.

Shipley Institute of Living Scale. All participants will complete the Shipley Institute of Living Scale (SILS) remotely or in-person as part of the Intake session. The SILS is a self-administered test designed to assess general intellectual functioning in adults and adolescents and to aid in identifying cognitive impairments [58]. The scale consists of two subtests, a 40-item vocabulary test and a 20-item test of abstract thinking. The total administration time is 20 minutes (10 minutes per subtest). A trained member of the study staff will score the test. The SILS correlates with the Wechsler Adult Intelligence Scale-Revised (WAIS-R) Estimated IQ Test and is considered a highly reliable assessment tool; with a good total score internal consistency (Cronbach's alpha= .92).

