Liver Function, Gamma-glutamyl Transpeptidase, and Creatinine tests. One 8.5ml blood sample will be drawn at the Intake visit. Blood will be collected and placed in a serum-separator tube (SST) and mixed thoroughly. Samples will be centrifuged at 3100 rpm for 10 minutes. If separation is not complete, the sample will be centrifuged at the same RPM for an additional 5 minutes. The following chemistry will be assessed:

1. Total protein.
2. Albumin.
3. Globulin.
4. Albumin/Globulin ratio.
5. Bilirubin (total, conjugated and unconjugated)
6. Aspartate amino transferase (AST).
7. Alanine amino transferase (ALT).
8. Alkaline phosphatase (AP).
9. Gamma glutamyl transferase (Gamma-GT)
10. Creatinine.

Neuroinflammation. Blood samples will be collected at Baseline and Pre-Quit Testing visits to explore the association of biomarkers of neuroinflammation using a 6 cytokine assay (e.g., C-Reactive Protein; Interleukin-6) with smoking status and cognition (HIV+ group only). Whole blood will be collected in two EDTA tubes and two SST tubes at each visit and delivered to the Laboratory Biomarkers, Quantitative Pharmacology, Neuroimaging, and Neurobehavioral Characterization Core at the Penn Mental Health AIDS Research Center for storage and analysis.

Blood Glucose. Because metformin may lower blood glucose, glucose levels will be measured at each in-person study visit. As recommended by the National Institute of Diabetes and Digestive and Kidney Diseases (NIDDK), blood glucose levels in non-diabetic individuals less than 70 mg/dl may indicate hypoglycemia. The Abbott Precision Xtra Blood Glucose & Ketone Monitoring System will be used to measure blood glucose (https://freestyleserver.com/Payloads/IFU/2017july/ART24315-002_rev-A_WEB.pdf). This device is indicated for home

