and professional use. As recommended by the manufacturer, the device will be cleaned and disinfected after each use. A trained member of the research staff will obtain a drop of blood (approximately 0.3 microliter) via a finger prick using a lancing device. The device provides a blood glucose reading within 60 seconds. Individuals who have a blood glucose level less than 70 mg/dl will be provided a beverage containing 15 g of carbohydrate (e.g., fruit juice or soft drink) and asked to wait in the laboratory. After 15 minutes, blood glucose will be rechecked to ensure it is greater than 70 mg/dl before allowing the participant to leave. Participants who present with blood glucose less than 70 mg/dl may be withdrawn from the study.

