4.3 Recording of Adverse Events

At each contact with the subject after the Intake, the study research assistant will seek information on adverse events by specific questioning using a side effect checklist and, as appropriate, by examination. Side effects will be monitored through a two-pronged approach. First, participants will complete a side effects checklist (SEC) at each study visit after the Intake reporting with a frame of reference since their last study visit. The SEC will assess the frequency and severity of common side-effects associated with metformin. These items will be rated by participants on a 0 (none) to 3 (severe) scale, and can be summed to provide an overall side effects index. Participants will also complete a non-structured, open-ended question (SEC Open-ended) at each study visit with a one week frame of reference to assess if participants are experiencing any additional symptoms or medical concerns that may be related to their participation in the study. Trained staff will review participant responses and collect additional information as needed from the participant.

Research staff are trained to inquire (time of onset, nature of issue reported, possible relation to metformin treatment, review of previously reported side effects or concerns, etc.) about any notable side effects or medical concern reported by participants. Any severe (or a pattern of moderate) side effects or notable medical concern will be reported to the Project Manager, Study Physician, and PI/Co-I to determine a course of action (e.g. continue to monitor, reduce medication, stop medication). This consult, including all relevant information, will be documented via email. The Study Physician is knowledgeable of side effects related to metformin and is qualified to manage possible side effects.

Based on published reports using the 500 and 1500 mg doses of metformin we expect few side effects and we expect these side effects to be mild and transient in nature. However, in the unlikely event of an adverse event (AE) the study physician/investigator will determine the severity of the AE, the relationship of the event to the study drug and decide the course of action for the study subject. The study physician/investigator will determine the relationship of toxicity of the study medication as not related, possibly related, probably related, or definitely related using standard criteria.

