The importance of this research outweighs the risks to subjects, which are minor. There is minimal risk for serious adverse events. The treatments and procedures used in this study have been shown to be relatively safe. Numerous clinical trials have demonstrated the safety and efficacy of metformin. Research staff will monitor subjects closely during their participation. Data from this project will serve as preliminary data to formally test metformin as an adjunct medication to smoking cessation treatment.

SUBJECT COMPENSATION

Participants will receive compensation for each session they complete and can receive up to \$280 for completing all study requirements (including travel reimbursement). In place of \$10/session to cover travel expenses, subjects may elect to use a round-trip car ride service (i.e., Lyft) which will be arranged and paid for in full by the research study. If they choose to use the ride service, they will not receive \$10 for travel reimbursement and their total visit compensation will be up to \$240. Travel will not be reimbursed for sessions designated as “in-person”, if they have to be completed by phone.

Task completion compensation will depend on participants arriving on time for study visits and following study instructions. If they do not follow instructions, task completion compensation may be withheld.

The Greenphire ClinCard will be the primary form of payment for this study. The ClinCard is a reloadable, pre-paid card for the purposes of compensation. Compensation will be loaded onto the ClinCard within 24 hours of completed visits. Staff may ask participants to provide a Social Security Number, or complete a W-9 for this purpose, after determining eligibility so that a ClinCard can be assigned. Clincards may be mailed to subjects following the eligibility determination for the study.

If a subject is found ineligible at any session due to any of the above-mentioned criteria, they will only be compensated \$10 for travel, unless they have elected to use the ride service for that session.

Subjects who successfully refer others to the program (i.e., person referred to program completes initial phone screen) will be awarded \$20 per referral, for a maximum of 3 referrals. Compensation distribution is shown in the table below:

Day	Study Visit	Visit Compensation	Task Completion	Travel ³	Bonus	Total
-1	Intake	\$20	-	\$10		\$30
0	Baseline	\$30	\$10	\$10		\$50
7	Remote Check-In	\$10	\$10			\$20

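### A low glucose reading on study drug can remove a participant before the Day 23 primary outcome, and the plan names nobody to decide

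*Combined protocol and SAP*

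**What the plan says.** The plan has three rules for the same event.

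- **Key Exclusion Criteria.** The list opens with "Subjects who self-report and/or present with the following criteria will not be eligible to participate in the study". Medical item 11 reads "A blood glucose level less than 70 mg/dl at any visit".
- **Section 3.1, Blood Glucose.** A participant with a low reading gets a carbohydrate drink, waits, and is rechecked after 15 minutes before leaving. The text then adds: "Participants who present with blood glucose less than 70 mg/dl may be withdrawn from the study". It does not say who decides, on what grounds, or whether a normal recheck settles the matter.
- **Study Visits.** The Baseline and Day 23 steps call for the drink and nothing more. Day 21 repeats the Baseline activities.

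The same section explains the monitoring: "Because metformin may lower blood glucose, glucose levels will be measured at each in-person study visit". Table 1 schedules glucose at Baseline, Day 21 and Day 23. Under Design, the high-dose arm is escalated as "500 mg q.d (days 1-7); 1000 mg q.d (days 8-14); 1500 mg q.d (days 15-23"), so it takes 1500 mg from Day 15.

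For raised blood pressure after Intake, section 3.1 is explicit: "the Study Physician or Study PI will be consulted to discuss whether the participant should continue taking the study medication". Section 4.1 ends enrolment when 84 subjects have completed every requirement. The Statistical Analysis section plans summary statistics and effect-size estimates without formal tests. It names no analysis set and does not say how withdrawn participants are handled.

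**The concern.** A safety rule for hypoglycaemia is proper. The difficulty is that the plan ties it to leaving the study, when the safety question is only whether to stop the drug.

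At Days 21 and 23 the criterion is measured after randomisation, on a variable that treatment may move. Removal could therefore be more common in one arm than another. A participant removed at Day 21 gives no mood or cognition data under abstinence. One removed at Day 23 may give none either. Because accrual is counted in completers, enrolment continues past each removal, and the completing group could be partly selected by treatment.

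The pilot exists to produce effect-size estimates for a later trial and to explore whether 1500 mg adds benefit without added adverse effects. Arm-related removal bears on both. The unclear wording adds a practical risk: two staff members could handle the same reading differently.

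**Working it through.** **1. The plan's own figures.** The documents give no low-glucose rate. The only statistical figures are the precision statements for 18 per group, and both reproduce:

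- Mean: t(0.975, 17)/√18 = 0.497 SD, inside the stated half SD.
- Correlation at r = 0: 2·tanh(1.96/√15) = 0.934, inside the stated 0.94.

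With 17 in a group the same formulas give 0.514 SD and 0.961, so both limits would be missed. Since accrual runs to completers, however, the issue is selection rather than lost numbers.

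**2. The rules side by side.** The exclusion list is mandatory in wording. Section 3.1 is permissive. The visit steps treat and then go on to questionnaires and cognitive tasks. The natural combined reading is that withdrawal is discretionary. Even so, what is left to discretion is removal from the study, and no glucose text says whose discretion it is.

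**3. Exposure to drug.** Three readings are scheduled and two follow the first dose. Doses are taken with the evening meal. With none missed, the high-dose arm has had this many 1500 mg doses:

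- By the Day 21 visit: Days 15 to 20 = 6, or 7 if the visit follows that day's dose.
- By the Day 23 visit: Days 15 to 22 = 8, or 9 on the same basis.

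The low-dose arm has had 500 mg daily and the placebo arm none. These counts show exposure. They do not show how many people would be removed.

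**4. What is lost.** Removal at Day 21 forfeits the Day 23 session. At Day 23, glucose is listed as step 4, ahead of the mood questionnaires (step 7) and the cognitive battery (step 9).

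**5. Timing of randomisation.** The text under Final Eligibility Phone Call places randomisation before the Baseline session. Design and Procedures place it after the Day 0 visit. On the first order even the Baseline reading follows randomisation, although it still precedes the first dose and so cannot be affected by the drug.

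**6. Illustrative size, on assumed inputs.** Suppose the lowest-glucose fraction q of an active arm is removed and nobody on placebo, and glucose correlates r with the outcome. With both normally distributed, the active-arm mean shifts by r·φ(z_q)/(1−q):

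| q | r | Shift (SD) |
|---|---|---|
| 0.02 | 0.1 | 0.1 × 0.0484/0.98 = 0.005 |
| 0.05 | 0.3 | 0.033 |
| 0.10 | 0.3 | 0.058 |
| 0.20 | 0.5 | 0.5 × 0.2800/0.80 = 0.175 |

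Neither q nor r comes from the documents. The range from 0.005 to 0.175 SD shows only that even the extreme corner lies well inside the 0.497 SD half-width for one arm's mean.

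**The case against.** The strongest reply is that the operational text already gives discretion. Section 3.1 is the only place that says what follows a low reading on study, and it is permissive. No visit step orders removal. The drug screen is built the same way, with a list item covering testing sessions and a permissive consequence at the visits. Item 11 can be read as the trigger and section 3.1 as the consequence. This largely stands. A reader might infer that item 11 makes withdrawal automatic and shuts out a physician's decision; the documents do not support that.

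A reader might also infer that glucose is the odd one out among criteria that otherwise allow judgement. That is too broad. The drug-screen item allows judgement only for a suspected false positive. For blood pressure after Intake the discretion comes from section 3.1, as it does for glucose. The true difference is narrower: the blood-pressure text names who decides and makes study drug the subject of the decision, and the glucose text does neither.

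Section 4.3 offers a general route, sending notable medical concerns to the Project Manager, Study Physician and PI/Co-I "to determine a course of action (e.g. continue to monitor, reduce medication, stop medication"). Glucose is not named there, but nothing excludes it. The compensation clause beginning "If a subject is found ineligible at any session due to any of the above-mentioned criteria" governs payment and does not establish that a low reading on drug makes someone ineligible.

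Finally, the risk section describes metformin as well tolerated in people without diabetes, and section 4.3 expects few side effects. Removals may be rare. This stands and limits the weight of the point.

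**Conclusion.** The point holds in a limited form. The exclusion list and section 3.1 disagree. Section 3.1 probably reflects the intent, but it leaves the decision-maker unnamed. On either reading the plan permits removal from the study, before the Day 23 outcomes are complete, on a variable that treatment may affect, with accrual continuing to 84 completers.

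The documents do not allow the bias to be sized or signed. It is probably small, in a pilot with no formal testing. A reader might go further and conclude that the arm estimates will be materially biased, that removed participants are replaced arm by arm, or that their data are dropped from the analysis. The documents support none of these: they give no event rate, describe no arm-specific replacement, and define no analysis set. The point rests on the protocol's own statement that metformin may lower glucose, and on removal meaning that later outcomes are not collected. It is worth correcting because the correction is cheap, not because a large effect has been shown.

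**What to change.** 1. Limit item 11 to the Baseline reading, which precedes the first dose. Complete that check before randomisation, following the order in Design and Procedures, and bring the Final Eligibility Phone Call text into line.
2. For Days 21 and 23, replace the withdrawal sentence in section 3.1 with the blood-pressure model. Give the drink, recheck at 15 minutes, and have the Study Physician or PI decide whether study drug stops.
3. Still collect the Day 21 and Day 23 outcomes where safe, and analyse these participants in their randomised arm.
4. Add one CRF flag for sessions at which the drink was given.

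The cost is protocol wording and the flag. The drink and recheck already exist, so the safety steps are unchanged. The downside is a few observations taken off drug or after a carbohydrate drink, which the flag and the drug-stop record make identifiable. This does not address other removals after randomisation, such as those for three or more missed doses or for smoking during the abstinence period.

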Final Eligibility is defined as: Liver function test results and GGT liver enzyme levels that are no more than 20% outside the normal, clinical range and serum creatinine levels less than 1.5 mg/dL [males], less than 1.4 mg/dL [females]]. Albumin/Globulin ratios 20% outside of normal range will be evaluated for clinical significance by the Study Physician and eligibility will be determined on a case-by-case basis.

Eligible subjects will confirm the study schedule and be randomized to a medication group. Ineligible subjects may be referred to other studies at our center.

- **Baseline Session (Day 0).** Participants will complete a 1.5-hour Baseline session before starting study medication. The Baseline session must be scheduled at least 2 days after Intake, but no more than 30 days can elapse between Intake and Baseline. At the Baseline session participants will:
 1. Provide a CO sample.
 2. Provide urine specimens for drug and (if applicable) pregnancy tests. Participants who test positive for the urine drug screen may be withdrawn from the study. Participants believed to have a false-positive result may continue in the study, with investigator approval.
 3. Complete a blood pressure measurement (See Blood Pressure Procedures under Screening/covariate measures).
 4. Have their blood glucose measured via a handheld glucose monitoring test (see Measures: Screening/Covariates). Subjects who have a low blood glucose level (i.e., less than 70 mg/dl) will be provided a beverage containing at least 15 g carbohydrates (e.g., 4 oz of fruit juice).
 5. Provide two 10 ml and 2 8.5 ml blood samples (less than 3 tablespoons) for examining biomarkers of neuroinflammation (HIV+ subjects only).
 6. Complete questionnaires (smoking rate, concomitant medication review, withdrawal, smoking urges, mood, subjective effects, and side effects). *
 7. MADRS, YMRS, Bipolar Disorder Additional Screener, if necessary*
 8. Complete cognitive tasks which may include tasks assessing working memory (n-back), verbal learning memory (HVLT-R), cognitive flexibility (color shape task), response inhibition (stop-signal task), and delay discounting.

9. Be given instructions for study medication. Medication may be mailed to the participant or provided at the session.

* Some tasks may be completed remotely to reduce the length of in-person visits.

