Suicidal Behavior and Ideation (C-SSRS). All participants will complete the C-SSRS (Screening Version) with a trained staff member remotely or in-person. The C-SSRS is a structured interview that assesses the suicidal behavior and suicidal ideation in subjects [56, 57]. Occurrence of lifetime suicidal behavior is defined as having answered "yes" to at least 1 of the 4 suicidal behavior sub-categories (actual attempt, interrupted attempt, aborted attempt, and preparatory acts or behavior). Current suicidal ideation is defined as having answered "yes" to at least 1 of the suicidal ideation sub-categories (wish to be dead, non-specific active suicidal thoughts, active suicidal ideation with any methods without intent to act, active suicidal ideation with some intent to act [without specific plan], and active suicidal ideation with specific plan and intent) over the past month.

Carbon Monoxide. Carbon monoxide (CO) measures will be made using a Vitalograph Breath CO Analyzer (McNeil International, Inc., Lenexa, KS). The manufacturer will have calibrated this device within the past year. A new, disposable cardboard mouthpiece will be provided for each participant. The device has a digital screen which reports CO levels in parts per million (ppm). Participants will be asked to provide a CO breath sample by taking a large breath, holding their breath for two seconds, releasing the breath, then taking another deep breath and holding their breath for 10 seconds, as per the recommendations of the American Thoracic Society. Then, when instructed to do so, participants will exhale as forcefully and as long as they are comfortably capable. The largest value displayed is recorded during all CO breath samples. CO breath samples will be collected at each in-person study visit.

Blood Pressure. At the Intake, participants presenting with elevated blood pressure (i.e., systolic blood pressure greater than 159 and/or diastolic blood pressure greater than 99) will have a second blood pressure reading taken after a ten-minute period in which the participants will be instructed to sit comfortably. If, after the second reading, systolic blood pressure remains greater than 159 and/or diastolic remains greater than 99, the participant will be ineligible for the study, unless determined otherwise by the Study PI/Co-I or Study Physician, upon review.

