The Project Manager, PI ([name])/Co-I and Study Physician will work together to confirm eligibility criteria. The Study Physician/Nurse Practitioner and PI ([name])/Co-I will review charts for each subject and will document reviews by signing and dating the final eligibility checklist in each chart, and the medical history and physical form.

The research staff and Project Manager will ensure all medication is properly ordered and received from IDS, stored at the center, labeled, and distributed to subjects.

The data managers will be responsible for creating all CRFs and ensuring that all data will be entered and stored in a manner consistent with the design of the approved CRFs. They will also be responsible for developing the data entry/quality control producers for this study.

Enrollment will be complete when 84 subjects complete all study requirements. On average, 3-4 subjects will be enrolled per month. During the course of the study, safety and data quality monitoring will be performed on an ongoing basis in accordance with the University of Pennsylvania Sponsor-Investigator Standard Operating Procedure PM 004 and any

findings will be reviewed on a regular basis with the Investigators at the regular study meeting. The monitoring will include a regular assessment of the number and type of serious adverse events. The first monitoring day will occur no more than two weeks after the first subject is entered.

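### The exclusion footnote requires both systolic and diastolic pressure to be high at the second Intake reading, while the measures section excludes if either is high

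*Combined protocol and SAP*

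**What the plan says.** Under Characteristics of the Study Population, 4. Key Exclusion Criteria, Medical, item 8 excludes on either component: "Uncontrolled hypertension (BP systolic greater than 159 and/or diastolic greater than 99". An asterisk leads to a footnote with two steps.

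- The first step decides who is measured again after a 10-minute rest, and it is either/or: "Participants presenting with SBP greater than 159 mmHg and/or DBP greater than 99 mmHg at the Intake visit".
- The second step decides who is excluded, and it joins the limits with *and*: "If, after the second reading the SBP greater than 159 mmHg and the DBP greater than 99 mmHg". Such a person is ineligible unless the PI/Co-I or Study Physician decides otherwise.

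Under Study Procedures, section 3.1 (Blood Pressure) describes the same Intake sequence with the same override. Its decision sentence is either/or: "systolic blood pressure remains greater than 159 and/or diastolic remains greater than 99, the participant will be ineligible for the study". For later in-person visits the threshold is again either/or, but the consequence differs: "systolic blood pressure remains greater than 159 and/or diastolic remains greater than 99, the Study Physician or Study PI will be consulted".

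**The concern.** The footnote and section 3.1 govern the same decision about the same person and disagree. A staff member working from the exclusion list and another working from the measures section could reach opposite conclusions from one reading.

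This is a safety rule. Followed literally, the footnote lets someone with isolated systolic or isolated diastolic elevation leave Intake without the specific decision that section 3.1 calls for, namely ineligible unless a PI/Co-I or the Study Physician rules otherwise. The override does not repair this. In the footnote it applies to people who have already become ineligible, and a person with one raised component never reaches that point.

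**Working it through.** No arithmetic applies beyond a count and a truth check. The inputs are all the places where the protocol states the 159/99 limits.

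| Place | Step | Connective | Consequence |
|---|---|---|---|
| Key Exclusion Criteria, item 8 | criterion itself | and/or | excluded |
| Item 8 footnote | first Intake reading | and/or | repeat reading |
| Item 8 footnote | second Intake reading | **and** | ineligible, override possible |
| Section 3.1, Blood Pressure | first Intake reading | and/or | repeat reading |
| Section 3.1, Blood Pressure | second Intake reading | and/or | ineligible, override possible |
| Section 3.1, Blood Pressure | first reading, later visits | and/or | repeat reading |
| Section 3.1, Blood Pressure | second reading, later visits | and/or | consultation |

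Count: 7 statements, of which 6 use *and/or* and 1 uses *and*.

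Next, the two rules for the second Intake reading are applied to four example readings:

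| Second reading | SBP > 159 | DBP > 99 | Section 3.1 (either) | Footnote (both) |
|---|---|---|---|---|
| 180/105 | true | true | ineligible | ineligible |
| 150/90 | false | false | not excluded | not excluded |
| 180/95 | true | false | ineligible | not made ineligible |
| 150/105 | false | true | ineligible | not made ineligible |

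The rules agree when both components or neither component is high. They disagree exactly when one is high.

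The remaining question is what catches such a person afterwards.

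1. The Final Eligibility Phone Call (Study Procedures, 2. Study Visits) defines final eligibility by liver tests, GGT and creatinine, with no blood pressure term. It then says: "Eligible subjects will confirm the study schedule and be randomized to a medication group". On that text the person could be randomized before any further blood pressure check. Study Design, 2. Design and Study Procedures, 1. Procedures instead place randomization after the day 0 visit, so the order is itself unclear.
2. The Baseline Session, held before the first dose, includes a check: "Complete a blood pressure measurement (See Blood Pressure Procedures under Screening/covariate measures". The rule for visits after Intake then applies. It is either/or but triggers a consultation about study medication, not default ineligibility.
3. Section 4.1 (Data and Safety Monitoring Committee) says the physician or nurse practitioner and the PI/Co-I "will review charts for each subject and will document reviews by signing and dating the final eligibility checklist". This is a real safeguard, but a reviewer who applies the footnote could pass the person.

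**The case against.** The strongest reply is that item 8 still excludes. The footnote says who is ineligible; it never says that someone with one raised component is eligible. A repeat reading of 180/95 meets item 8 on its face and is excluded by section 3.1, so passing the person means reading the footnote as an implied permission. This has some force, and it confirms the intent. It does not remove the conflict. Item 8 says nothing about a repeat reading, its asterisk sends staff to the footnote for that step, and the footnote gives a different default from section 3.1.

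A second reply is that the six-to-one count overstates the case, because only two sentences govern the second Intake reading and they split one to one. That is correct as to the conflict. The count serves only to show which version was meant.

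A third reply is that the risk is small, and most of this stands:

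- Telephone screening already gives mild hypertension as an example of a condition needing physician clearance.
- A medical professional leads a physical examination at Intake.
- Both versions of the rule allow an override.
- The metformin side effects listed under Potential Study Risks include no blood pressure effect.
- The order of randomization and Baseline does not alter drug exposure, since the Baseline check precedes dosing either way.

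The sentence also lacks a verb, which suggests a drafting slip and not a deliberate choice. These points limit the consequence. They do not make the sentence right.

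**Conclusion.** The concern holds. The footnote's decision sentence is wrong as written: it conflicts with section 3.1 on the same step and with the criterion it is meant to qualify. That *and/or* was intended is an inference from the other six statements and from the absence of any stated reason for a looser rule on repeat measurement.

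The effect is confined to Intake applicants whose second reading has exactly one component above its limit. The documents give no prevalence, so the number cannot be estimated. No outcome, estimate or sample-size figure depends on it, and later checks limit the harm. It should still be corrected, because it is a safety threshold in the list that staff use to decide eligibility.

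**What to change.** In the footnote to item 8, replace *and* with *and/or* between the systolic and diastolic limits in the second-reading sentence, and supply the missing verb (*remains*) before each limit so that it matches section 3.1. Leave the PI/Co-I or Study Physician override as it is.

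The cost is a correction to one sentence. A few more applicants may be excluded at Intake or referred for review, which is what section 3.1 already requires.
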